1.3 Secondary Objectives

1.3.1 To determine safety of HCQ and Azithro including 1) adverse events (AEs) leading to early discontinuation of treatment with HCQ and Azithro and 2) cardiac AEs.

1.3.2 To determine if HCQ and Azithro reduce the frequency of detection and levels of SARS-CoV-2 RNA in site-collected nasopharyngeal (NP) swabs and self-collected nasal swabs in subset of participants.

1.3.3 To determine if HCQ and Azithro change the severity and duration of self-reported symptom experience of COVID-19.

1.3.4 To determine if HCQ and Azithro will prevent the composite endpoint of either hospitalization or death by 24 weeks after study entry. Hospitalization is defined as ≥ 24 hours of acute care.

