The investigators reported no biologically significant effect on mean alternans. In fact, when combined, Azithro reduced the magnitude of alternans observed with chloroquine alone. This preclinical data is supported by clinical studies using chloroquine with Azithro. The Kimani et al. study evaluated malaria prevention during pregnancy where 1445 women received 3 days of chloroquine plus Azithro that was repeated at 4-8 week intervals during the second and third trimesters of pregnancy. Although QT intervals were not assessed at baseline or throughout the study, there were no reported cardiac AEs [29]. Sagara et al. conducted two randomized, comparative, non-inferiority studies in Africa where patients with malaria received Azithro 1000 mg (n=227) or Azithro 500 mg (n=9) with chloroquine 600 mg, all once daily for 3 days [49]. While QT interval was not measured at the beginning or during the study, there were no cardiac AEs noted. While subjective adverse events of dizziness and palpitations were reported, they occurred no more frequently than seen in the mefloquine control arm. **The azithromycin label reports that, in comparison to chloroquine alone, the maximum mean (95% upper confidence bound) increases in QTcF are 5 (10) ms, 7 (12) ms, and 9 (14) ms, with the co-administration of 500 mg, 1000 mg, and 1500 mg azithromycin, respectively.**

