Given that the proposed study will exclude those taking **concomitant** medications with high risk of prolonging QT ([section 5.4.1](#)), we do not feel that electrocardiograms (EKGs) at study entry or during treatment are needed. **We believe that** exclusions on the basis of baseline QTc are unlikely to add significantly to **overall safety, above and beyond the planned exclusion** of participants with higher risk for drug-induced ventricular arrhythmias and cardiac events **based upon** relevant personal or family cardiac history, high risk clinical history including severe renal and liver disease, and those who are taking additional QTc prolonging agents. Further, in the midst of a global pandemic, the risk-benefit assessment must consider a wide range of participants, study staff and resource utilization-related issues. In this case, the condition of TdP is expected to be very rare and the performance of EKGs would require the use of personal protective equipment (PPE), for which supplies must be carefully preserved as the current pandemic escalates, and the risk of additional direct contact between staff and highly infectious study participants. As a result, we feel that the potential benefit of HCQ plus Azithro treatment for a disease with an overall case fatality rate of up to 3% (and based on preliminary estimates in the US, 3-11% among persons aged 65-84 years) outweighs the very small risk of a treatment-related cardiac AE, and therefore do not feel that EKGs at study screening or during treatment would be justified [50, 51].

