6.3.6 Clinical Assessments

No physical exams will be conducted.

Site clinical investigators will perform a clinical assessment at enrollment **for all participants**. In their clinical judgment, they may identify some participants who are ill enough to warrant further clinical evaluation, which may result in hospitalization. They will then refer these participants for such evaluation. These participants will not start study treatment, and not be included in the analyses. While clinical judgement may not be standard across sites, the process should balance site variation.

Post entry, see [section 8.4](#) for collection requirements for pregnancy.

Refer to [section 7.2](#) for AE collection requirements.

Concomitant Medications

Post-entry, the following new and discontinued concomitant medications must be recorded:

- High blood pressure medications
- Steroids or other immunosuppressive or immunomodulatory medication
- Non-steroidal anti-inflammatory drugs (NSAIDs)
- Chemotherapy
- Antibiotics, antifungals and antivirals (including antiretrovirals)
- HCQ or chloroquine or any agent felt to have potential COVID-19 activity
- Inhalers
- Agents with QTc prolongation potential and antiarrhythmics listed in [section 5.4.1](#).

Study Treatment (Intervention) Modifications

Record any modification to treatment, treatment interruption, and permanent discontinuation of treatment, and the reason for the modification, interruption, or discontinuation.

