7.2 Adverse Event Collection Requirements for This Protocol

Post-entry, all AEs must be recorded on the eCRFs within 72 hours if any of the following criteria have been met:

- All Grade ≥ 3 AEs
- All cardiac AEs regardless of grade
- All AEs that led to a change in study treatment/intervention regardless of grade
- All AEs meeting SAE definition or EAE reporting requirement

NOTE: SAEs or events meeting EAE reporting requirements should also be entered into the DAIDS Adverse Experience Reporting System (DAERS), an Internet-based reporting system.

All AEs that are reported must have their severity graded. To grade AEs, sites must refer to the DAIDS AE Grading Table, corrected Version 2.1, July 2017, which can be found on the DAIDS RSC website at <https://rsc.niaid.nih.gov/clinical-research-sites/daims-adverse-event-grading-tables>.

Serious Adverse Events (SAEs)

An SAE is defined as any untoward medical occurrence that:

- Results in death
- Is life-threatening illness
- Requires inpatient hospitalization or prolongation of existing hospitalization
- Results in persistent or significant disability/incapacity
- Is a congenital anomaly/birth defect.
- Is an important medical event that may not be immediately life-threatening or result in death or hospitalization but may jeopardize the patient or may require intervention to prevent one of the other outcomes listed in the definition above).

Ventricular arrhythmias, cardiac events requiring intervention or hospitalization, and deaths should be reported as soon as possible but no later than 24 hours to the A5395 Clinical Management Committee (CMC; e-mail: [contact]). If known, sites should indicate if the death was a sudden cardiac death. Sudden cardiac death is defined in this study as unexpected death from a cardiac cause within 1 hour of onset of symptoms OR found dead without clear explanation.

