10.2.2 Secondary Outcome Measures

- 10.2.2.1 Death from any cause during the 21-day period from and including the day of the first (confirmed) dose of study treatment.
- 10.2.2.2 Death from any cause or hospitalization or urgent visit to an emergency room or clinic during the 21-day period from and including the day of the first (confirmed) dose of study treatment.
- 10.2.2.3 Death from any cause or hospitalization during the 24-week period from and including the day of the first (confirmed) dose of study treatment. Hospitalization is defined as requiring at least 24 hours of acute care in a hospital or similar acute care facility, including Emergency Rooms or temporary facilities instituted to address needs during the COVID-19 pandemic. Evaluation at a hospital or similar facility with less than 24 hours of acute care is not considered a hospitalization.
- 10.2.2.4 Premature discontinuation of study treatment due to an adverse event.
- 10.2.2.5 Occurrence of any cardiac adverse events from start of study treatment through Day 20.
- 10.2.2.6 Duration of fever defined as the last day in the participant's daily diary card on which a temperature greater than 100.4°F was recorded or a potentially antipyretic drug, such as acetaminophen or ibuprofen, was taken.
- 10.2.2.7 Duration of symptoms associated with COVID-19 disease defined as the last day in the participant's daily diary card on which a moderate or worse symptom was recorded. The set of targeted symptoms are the same ones that are used in many influenza studies, with the addition of the symptoms of loss of smell and loss of taste, which have been associated with COVID-19 infection. The symptoms from influenza studies are: cough, shortness of breath, feeling feverish, fatigue, muscle aches, diarrhea, vomiting, nausea, headache, sore throat, nasal obstruction (stuffy nose), and nasal discharge (runny nose). These symptoms are listed individually on the Study Diary that each participant will complete each day. The scoring is that used in influenza studies, whereby participants grade each symptom as absent (score 0), mild (1), moderate (2), or severe (3).
- 10.2.2.8 **Participant-specific area under the curve (AUC) of the symptom**

score associated with COVID-19 disease **over time (through Day 20)** defined as the sum of scores for the targeted symptoms (defined above) in the participant's daily diary record (each individual symptom is scored from 0 to 3).

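### Any-grade cardiac adverse events are compared between arms without EKG or physical exam, yet the protocol does not require participants to be asked about palpitations, fainting or dizziness

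*Protocol*

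**What the plan says.** Protocol 1.3.1 makes safety a secondary objective, naming "adverse events (AEs) leading to early discontinuation of treatment with HCQ and Azithro and 2) cardiac AEs". The matching outcome, 10.2.2.5, is "Occurrence of any cardiac adverse events from start of study treatment through Day 20", and 10.6.2 compares its proportion between arms by binary regression adjusted for risk stratum. Section 7.2 collects "All cardiac AEs regardless of grade". Other events are recorded only if they are Grade 3 or higher, change study treatment, or meet the serious or expedited criteria.

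Objective cardiac assessment is ruled out. Section 2.1 states "we do not feel that electrocardiograms (EKGs) at study entry or during treatment are needed". Section 2.2 (Mitigation of Risk) considers mobile ECG devices and declines them. Section 6.3.6 adds "No physical exams will be conducted".

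The daily Study Diary covers Days 0 to 20. Section 10.2.2.7 names its targeted symptoms as loss of smell, loss of taste and twelve items from influenza studies: "cough, shortness of breath, feeling feverish, fatigue, muscle aches, diarrhea, vomiting, nausea, headache, sore throat, nasal obstruction (stuffy nose), and nasal discharge (runny nose". Section 6.3.10 adds temperature, medications and major events such as emergency room or clinic visits and hospitalization.

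The Schedule of Evaluations (6.1) places a clinical assessment at entry and on Days 2, 4, 6, 9, 13, 17 and 20. Section 8.1 has adverse events assessed remotely, and 6.3.11 refers to a contact script in the MOPS.

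Palpitations are mentioned in the background, where section 2.1 says of two cited malaria trials that "there were no cardiac AEs noted. While subjective adverse events of dizziness and palpitations were reported".

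**The concern.** Without an EKG or examination, an arrhythmia that does not bring the participant to care will usually come to light only as a symptom: palpitations, an irregular heartbeat, fainting or near-fainting, or dizziness. The diary is the one instrument every participant is asked to complete daily, and the symptoms the protocol names for it were chosen for the COVID-19 symptom outcomes. The text does not require staff to ask about cardiac symptoms at the contacts either.

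Classification adds to this. A Grade 1 or 2 palpitation that a site calls cardiac must be recorded under 7.2. If it is called something else, and it is not serious or expedited and does not change treatment, it is not collected. Sites could reasonably differ.

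At stake is how a finding of no difference in cardiac events would be read. Section 2.1 says it is unknown whether the risks of this short course differ in COVID-19, so the comparison should be able to inform that question for milder events as well as for those that reach a hospital.

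**Working it through.** **1. Symptom count (10.2.2.7).** 12 influenza items + loss of smell + loss of taste = 14. Items naming palpitations, dizziness, fainting or chest symptoms: 0 of 14.

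**2. Contacts (6.1).** Days 2, 4, 6, 9, 13, 17 and 20 give 7 scheduled post-entry clinical assessments through Day 20. Collection is therefore not left to spontaneous reporting alone. What is asked at these contacts depends on the MOPS script, which is not shown.

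**3. Route by type of event, from the text available.**

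| Event | Route in the protocol |
|---|---|
| Ventricular arrhythmia; cardiac event needing intervention or hospitalization; death | Report within 24 hours to the clinical management committee (7.2); ventricular arrhythmias and such cardiac events also expedited (7.3.2); DSMB notified of torsades, ventricular arrhythmias and sudden deaths (10.5) |
| Event leading to an emergency room or clinic visit | Diary major-event entry (6.3.10) |
| Milder palpitations, near-fainting or dizziness at home | Not among the named diary symptoms; no required question at contacts; recorded under 7.2 if elicited and classed as cardiac, or if another 7.2 criterion is met |

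The gap is confined to the last row.

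**4. Size, as illustration.** The protocol gives no cardiac event rate, capture fraction or power for this outcome, so there is no stated figure to reproduce. Assume true symptomatic rates p1 and p2, 1000 per arm (10.4), a two-sided 5% test, and the same capture fraction f in both arms, so the observed rates are f·p1 and f·p2.

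Normal approximation: power = Φ{[d − 1.96·√(2·p̄(1−p̄)/n)] / √[(p1(1−p1)+p2(1−p2))/n]}, with d the difference and p̄ the mean of the two observed rates.

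- f = 1, 1% vs 3%: (0.02 − 1.96 × 0.00626)/0.00625 = 1.24, power 89%.
- f = 0.5, 0.5% vs 1.5%: (0.01 − 1.96 × 0.00445)/0.00444 = 0.29, power 61%.

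Events are few, so exact enumeration of the pooled two-proportion z test is preferable:

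| Capture fraction f | 1% vs 3% | 2% vs 4% |
|---|---|---|
| 1 | 91% | 76% |
| 0.5 | 64% | 46% |
| 0.25 | 33% | 24% |
| 0.1 | 14% | 12% |

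**5. Bias or precision.** With equal f, the ratio f·p2/(f·p1) = p2/p1 is unchanged. The absolute difference shrinks by the factor f (at f = 0.5, from 2 percentage points to 1) and expected events fall from 10 vs 30 to 5 vs 15. The main loss is sensitivity and precision.

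**The case against.** The strongest reply is that the protocol does schedule adverse event ascertainment. Staff make seven post-entry assessments through Day 20, three of them (Days 2, 4 and 6) during dosing, and 6.3.6 ties these to the collection rules of 7.2. The script may already ask about palpitations and fainting. The diary form sits on a data portal and is not shown; 10.2.2.7 says its listed symptoms are on the form, not that nothing else is. All of this stands. A reader might infer that the cardiac outcome rests on unprompted reports, but the documents do not support that.

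A reader might also infer from section 2.1, which sets palpitations apart from cardiac events, that this trial does not count them. That does not follow either. The sentence summarises cited trials, 7.1 counts a symptom as an adverse event, and no section tells sites to classify from background text. The sentence needs no correction on this account.

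The EKG decision is declared and reasoned: protective equipment, staff exposure, and a design settled in discussion with the regulator (2.1 and 2.2). It is not an error. Serious cardiac events have their own reporting routes.

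Finally, listing the terms that count as cardiac can be left to the SAP, and contact prompts to the MOPS. The first half stands, so a missing definition alone would not be a finding. But an SAP can only classify what was collected. Symptoms that nobody asked about cannot be recovered at analysis, and the protocol requires no such question.

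**Conclusion.** The point holds as an improvement to ascertainment. The trial makes any-grade cardiac adverse events a between-arm outcome, removes objective cardiac assessment, names no arrhythmia symptom among its 14 diary items, and does not require the contacts to ask about one. Milder events may therefore be captured incompletely and differently from site to site.

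The likely effect is lost sensitivity and precision rather than bias between arms, provided blinding keeps reporting similar in both. Serious events are largely outside the problem. The size cannot be fixed from the documents: the drop from 91% to 64% or 33% power depends entirely on assumed rates and capture fractions. The conclusion is also conditional on two documents not shown. If the diary form or MOPS script already asks these questions of everyone, what remains is to say so in the protocol and state what counts.

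**What to change.** 1. Check the Study Diary form and the MOPS contact script for questions on these symptoms.
2. If they are absent, add yes/no items for palpitations or irregular heartbeat, fainting or near-fainting, and dizziness to the daily diary and to the scripted contacts on Days 2 to 20, with identical wording in both arms.
3. Keep the items outside the 14-item symptom score, so that 10.2.2.7 and 10.2.2.8 are unchanged.
4. State in 7.2 and 10.2.2.5 which of the items count toward the cardiac outcome and at what grade.
5. Report each item by arm, separately from clinician-diagnosed cardiac events.
6. Leave the treatment-stop rules in 8.2 and 8.3 as they are. Both sections pair a stop for a cardiovascular event with a note that Grade 1 and 2 events require no change, so their wording must be reconciled with whatever definition is adopted.

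The cost is three diary items and some script wording, with no added visit, procedure or protective equipment. The drawback is some non-specific reports, especially of dizziness, from febrile participants in both arms; item-level reporting keeps these visible and apart from diagnosed events.

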2.2 Rationale

At present, there is no specific antiviral therapy for COVID-19. Few treatment studies have been conducted because most human CoV strains cause self-limited disease, and care is supportive. After SARS-CoV-1 was identified in 2002-2003 and caused a large global outbreak, there was an increased interest in the development of specific therapeutic agents. SARS-CoV-1 patients were treated with corticosteroids, type 1 IFN agents, convalescent plasma, ribavirin, and lopinavir or ritonavir; except for ribavirin, many of these agents have in vitro pre-clinical data that support their efficacy [52-67]. Since the SARS-CoV-1 outbreak in 2002-2003, new therapeutic agents targeting viral

entry proteins, proteases, polymerases, and methyltransferases have been tested; however, none of them has been shown to be efficacious in clinical trials [68-70].

Given the lack of specific antiviral therapy for SARS-CoV-2 infection, and the known safety profiles and ready availability of HCQ and Azithro as potential antiviral agents, **this regimen warranted further consideration. This, along with** some promise observed in pre-clinical and small clinical studies, **resulted in designing** this randomized, placebo-controlled trial **to** evaluate the efficacy and safety of HCQ and Azithro in persons who have active SARS-CoV-2 infection and mild to moderate COVID-19 symptoms.

Why HCQ and Azithro for COVID-19?

Mechanism: Since a putative antiviral mechanism for HCQ is alkalinizing of lysosomes [14, 15], there is good reasoning that Azithro can potentiate this activity because it also increases the pH of lysosomes, and has been documented to potentiate this effect with chloroquine. Given the extensive data from malaria studies, these drugs can be safely used together with no drug-drug interactions [29, 49] (see below).

French experience: There is a recent uncontrolled study by Gautret et al. that evaluated HCQ and Azithro for SARS-CoV-2 shedding. It was a 20-person single-arm study with SARS-CoV-2 infection in a hospital setting. The study evaluated 600 mg of HCQ daily, and Azithro was added to the HCQ treatment based on clinical status. Untreated patients from another center and cases refusing the protocol were included as negative controls. Presence and absence of virus at Day 6-post inclusion was the study end point. The authors showed that HCQ may be effective in reducing viral loads ([Figure 2.2-1](#)). Specifically, HCQ reduced the proportion of persons with SARS-CoV-2 infection with polymerase chain reaction (PCR)-positive samples by 75% in the 6-day period, and when it was combined with Azithro, it improved the treatment efficacy to 95% [13].

The same authors recently published on-line their experience with 80 patients, 6 of whom were in the original published cohort, admitted to their inpatient ward with documented SARS-CoV-2 infection [13, 71]. None of these individuals were originally admitted to **the** ICU, with 54% having evidence of lower respiratory tract infection and 5% being asymptomatic, and only 15% requiring supplemental oxygen at presentation. The **authors** reported that one died on their unit and one was transferred to **an** intensive care unit. **They** reported that 83% were nasopharyngeal swab PCR negative on Day 7 and 93% by Day 8. They further noted that 97.5% were culture negative by Day 5 of follow-up.

However, there are a number of limitations of the smaller study: 1) it was not randomized, 2) a therapeutic effect in the first 2 days of treatment is unusual as drug levels are unlikely to have achieved therapeutic levels, 3) the small number of participants, 4) the dropout rate in the treatment arm and exclusion from the analysis of a death and 3 ICU admissions, 5) the reliance on clearance of SARS-CoV-2 detected by NP swab as the primary outcome given the natural history, even in severe disease, is clearance of virus from the upper respiratory tract, and 6) lower baseline viral load in

persons receiving HCQ and Azithro, compared to the persons receiving HCQ alone. A secondary analysis of the data from this non-randomized trial was conducted and concluded that the data “show modest to no impact of HCQ treatment, with more significant effects from the HCQ-AZ combination, potentially suggesting a role for co-infections in COVID-19 pathogenesis. The trial of Gautret and colleagues, with consideration of the effect sizes, and p-values from multiple models, does not provide sufficient evidence to support wide-scale rollout of HCQ monotherapy for the treatment of COVID-19; larger randomized studies should be considered. However, these data do suggest further study of HCQ-Azithro combination therapy should be prioritized “as rapidly as possible” [72].

[figure not shown]

Figure 2.2-1: Clinical Course during HCQ and Azithromycin Treatment

The second larger study substantially increases the number of enrolled individuals, **but also** lacks a control group. It also enrolled a group with relatively mild disease, which is consistent with the population we plan to enroll and perhaps provides support for our strategy to use this regimen to prevent hospitalization in this subset of infected individuals.

Chinese experience: Reported clinical studies with these agents for COVID-19, apart from the Gautret studies, have been limited to chloroquine or HCQ and not Azithro or the combination. An initial report of clinical trials testing the safety and efficacy of chloroquine for the treatment of COVID-19 pneumonia across 10 hospitals in China noted that preliminary results from 100 patients suggested superiority of chloroquine phosphate to control treatment (control treatment unspecified), in outcomes including “inhibiting the exacerbation of pneumonia, improving lung imaging findings, promoting a virus-negative conversion, and shortening the disease course.” Further details are not available. Per this report, these initial findings have led to the recommendation that chloroquine phosphate be included in national Chinese guidelines for the management of COVID-19 [73].

An additional study of HCQ treatment in 30 “common” COVID-19 patients (reportedly with relatively mild disease) was published, with only the abstract available in English [74a]. In this study participants were randomized 1:1 to HCQ 400 mg po daily plus usual therapies vs usual therapies alone. All participants received inhaled interferon-alpha, and the majority in both arms (80% of the HCQ arm, 67% of the control arm) received umifenovir, and two participants in the control arm also received lopinavir and ritonavir. No difference in endpoints of PCR-negative Day 7 pharyngeal swabs, time to undetectable viral load, radiographic progression, and days to resolution of fever were observed. This small study was highly confounded by concomitant therapies and, thus the conclusions that can be made about the efficacy (or lack of efficacy) of HCQ are limited.

Future: Additional national and international trials of HCQ are underway or planned, largely in hospitalized patients, including a WHO trial (SOLIDARITY) comparing **five** treatment arms: chloroquine/HCQ, remdesivir, LPV/r, LPV/r plus interferon-beta, or standard of care; a European trial (DISCOVERY), with the same treatment arms as the WHO trial, but with HCQ only and not chloroquine or HCQ; an RCT of LPV/r **versus** HCQ in patients with mild disease (NCT04307693); an RCT of HCQ **versus** no HCQ in patients with mild or moderate disease, or asymptomatic (NCT04323631); HCQ **versus** placebo for COVID-19-related ARDS (NCT04315896); an RCT of various combinations of HIV protease inhibitors, oseltamivir, favipiravir, and HCQ (NCT04303299); a non-randomized trial of LPV/r **versus** HCQ versus baricitinib (janus kinase inhibitor) **versus** sarilumab (anti-IL-6 receptor antibody) (NCT04321993) for moderate to severe COVID-19 in hospitalized patients; a trial of remdesivir **versus** HCQ **versus** standard of care (NCT04321616); a randomized open-label trial of remdesivir, LPV/r, interferon beta, HCQ, or standard of care in hospitalized patients (NCT04315948); and multiple post-exposure prophylaxis trials of HCQ. Two unblinded studies of HCQ plus Azithro **versus** HCQ for COVID-19 pneumonia and hospitalized patients are planned in Brazil (NCT04321278, NCT04322123). Both of these trials are planning doses of HCQ 400 mg po BID and Azithro 500 mg po daily, one given for 10 days and one for 7 days.

Summary: The combination of HCQ and Azithro deserves further evaluation in a rigorous clinical trial in the outpatient setting. If we evaluate HCQ alone and find that it is no better than Placebo, then we have not answered the question if HCQ and Azithro is effective for COVID-19. Given the biologic rationale of potentiating raising lysosome pH [14, 15], then we would be left without a clear answer. However, if the proposed study shows that HCQ and Azithro is not better than Placebo alone, then we can be relatively confident that neither had an effect.

Further, the use of HCQ and Azithro can be implemented at scale through one outpatient visit or remote non-face-to-face visit at study entry. This will minimize contact between study participants and study staff to reduce use of PPE and potential risk of SARS-CoV-2 transmission.

Mitigation of Risk from HCQ and Azithro

HCQ can prolong the QT interval, and ventricular arrhythmias and TdP have been reported, but usually after prolonged administration [33], particularly in patients with

lupus and other comorbidities such as end stage renal disease [34-37]. **In fact**, drug-induced TdP and other life-threatening ventricular arrhythmias from HCQ are very rare and typically only observed at high doses given for long periods of time [14, 33, 38]. HCQ is a derivative of chloroquine, and the same molecule in both drugs causes the QTc prolongation; therefore, the use of chloroquine in malaria studies helps guide our reasoning with HCQ. When chloroquine was administered to healthy adults (regimen 600 mg + 600 mg + 300 mg on Days 1, 2, and 3, respectively) the average increase in QTc interval was 28 ms (18-38 ms; 95% CI) with no cardiac AEs reported [39].

The combination of short-course chloroquine and Azithro has been observed to be well tolerated in malaria trials. In particular, Kimani et al studied malaria prevention during pregnancy where 1445 women received 3 days of chloroquine plus Azithro that was repeated at 4-8 week intervals during the second and third trimester of pregnancy. Although QT intervals were not assessed at baseline or throughout the study, there were no reported cardiac AEs [29], which would be the main danger signal for TdP in such a study. Further, Sagara et al. conducted two randomized, comparative, non-inferiority studies in Africa where patients with malaria received Azithro 1000 mg (n=227) or Azithro 500 mg (n=9) with chloroquine 600 mg base, all once daily for 3 days **and there were no treatment-related cardiac events** [49]. Given the extensive experience in malaria prophylaxis and treatment, it is clear that any QT prolongation by either drug is not likely to be clinically relevant. In fact, the WHO explicitly states “Despite hundreds of millions of doses administered in the treatment of malaria, there have been no reports of sudden unexplained death associated with quinine, chloroquine or amodiaquine, although each drug causes QT/QTc interval prolongation” [38].

Despite the low risk of clinically relevant QT prolongation, the proposed study design incorporates a number of measures to further reduce the risk. These include the exclusion of people who take other agents known to prolong QTc, have a personal or family history of Long QT syndrome, a history of ventricular arrhythmias, known structural or ischemic heart disease, or severe kidney or liver disease.

The use of mobile devices that can perform ECG and measure vital signs has been discussed extensively by the study team and team leads have discussed the capabilities of select devices with their manufacturers or researchers who have used them. Based on these discussions, we have chosen to not include such monitoring for safety purposes for several reasons. Foremost, real-time monitoring for the large number of participants who will be enrolled at any one time will likely be unmanageable, and our older participants may have a harder time with such devices. Therefore, such monitoring is unlikely to lead to an immediate intervention. In addition, given the short duration of treatment and the long half-life of HCQ and Azithro, discontinuation of these drugs following detection of QTc prolongation, even if feasible, may have limited impact.

To help mitigate the risk of HCQ and Azithro causing TdP, we have followed the guidance from Simpson et al. [74b], which states, “minimizing exposure/contact: It may be reasonable to forego ECG screening to allow patients to remain in quarantine if no high-risk features exist (history of long QT syndrome, concomitant QT prolonging medications, structural or ischemic heart disease,

history of prolonged QTc on any ECG, history of abnormal renal function and/or electrolytes.” Therefore, we will exclude potential participants with underlying conditions associated with TdP, including: history of ventricular arrhythmia or on antiarrhythmics, personal or family history of long QT syndrome, history of hypomagnesemia or hypokalemia, history of structural or ischemic cardiac disease, use of antiepileptic or loop diuretic drugs, or use of drugs that can also prolong the QT interval. We will also have the close monitoring by the DSMB that can assist in quickly identifying safety issues with HCQ.

Overall, HCQ and Azithro are FDA-approved drugs that have the potential to decrease disease progression in early COVID-19 illness. HCQ shown anti-SARS-CoV-2 activity in vitro and there is a clear mechanistic pathway for Azithro to enhance HCQ activity. The combination has preliminary, though limited, non-randomized in vivo studies, as described above, to suggest candidacy as treatment for COVID-19. Rigorous clinical trials must be conducted to ascertain effectiveness and safety. These agents may be more likely to have an effect early in the course of SARS-CoV-2 infection and an intervention that decreases or prevent hospitalization would have substantial clinical, public health and economic impact. The proposed study is a multicenter, randomized, placebo-controlled study. As designed, it will be able to acquire rigorous data about the safety and efficacy of HCQ and Azithro compared to placebo for COVID-19 that will lead to generalizable evidence.

Justification for Dose

Doses of HCQ and Azithro are based on the pharmacokinetics of each drug, historical population pharmacokinetics models’ PK-QTc relationship, in vitro concentration-response relationship for HCQ, clinical PKPD model from persons treated for COVID-19 in the Gautret et al. study, the natural course of viral infection in humans and, finally, clinical trial simulations for efficacy and safety using all available pharmacological data [10, 71, 75-77]. **Further, this trial has been designed to approximate outpatient clinical practice. For outpatients with mild-to-moderate COVID-19 receiving HCQ and Azithro, an EKG would not be standard (nor would blood work). This, again, reflects a balance between the value of assessment and the risk of infection to healthcare workers (and study staff) in the setting of active and acute COVID-19. Thus, we have opted for a “no touch” research protocol for outpatient participants, and, in close discussions with the FDA and heeding their guidance, we have chosen doses of HCQ and Azithro that are commonly used in the outpatient setting with no laboratory or EKG monitoring.**

Justification for the Control Arm

In light of the heterogeneity of disease progression in those with COVID-19, it is extremely important that this study include a control group. To this end, this trial will have a double-blinded placebo control arm to best determine the efficacy and safety of HCQ and Azithro in the outpatient setting for persons with COVID-19.

Justification for Placebo Controlled Design

There is public interest in several putative therapeutic agents for COVID-19. However, the available data on efficacy and safety for each remains preliminary and limited. The

above-mentioned non-randomized trial of HCQ with and without Azithro signals a possible benefit of the combination but is far from conclusive, as highlighted by a recently performed secondary analysis of the study data. Further, as described, these medications are not without potential side effects. Given the absence of high-quality efficacy data and the potential risks, there is clear equipoise regarding the use of HCQ and Azithro for patients with COVID-19. A well-powered placebo-controlled trial will provide the best opportunity to recruit outpatients with COVID-19 and rigorously evaluate the safety and efficacy of these medications.

Justification for Age Restriction

Children and adolescents will not be included in this trial. Initial information about the epidemiology of COVID-19 indicates that the overwhelming burden of severe disease occurs among older adults, especially those with comorbidities. Given significant gaps in knowledge regarding SARS-CoV-2 infection in this population, and a low incidence of severe morbidity/mortality in children, the risk/benefits do not warrant inclusion of this population into this trial at this time.

Justification for Comorbidities

Individuals with comorbidities, such as diabetes and HIV, will be included, as they may have a higher risk of hospitalization and life-threatening COVID-19.

Justification for Pregnancy and Breastfeeding

The proposed doses of HCQ and Azithro have been used safely in pregnant women and women who are breastfeeding [29]; therefore, these persons will be eligible for the study.

